#### **6.2.2** Secondary Endpoint(s)

Efficacy in Excessive Daytime Sleepiness (EDS):

- Mean absolute change in the Epworth Sleepiness Scale (ESS) from baseline to the end of the 2-week treatment period.
- ESS clinical response, defined as ESS absolute decrease from baseline of at least 3.0 points, after 2 and 6 weeks of treatment.
- ESS clinical response, defined as ESS  $\leq$  10 after 2 and 6 weeks of treatment.
- ESS clinical response, defined as either ESS  $\leq$  10 after 2 and 6 weeks of treatment or ESS absolute decrease from baseline of at least 3.0 points after 2 and 6 weeks of treatment.
- Mean relative change in the Epworth Sleepiness Scale (ESS) from baseline to the end of the 2-week and 6-week treatment periods (percentage of absolute decrease compared to baseline ESS).
- Mean absolute change in the Scales for Outcome in Parkinson's Disease Sleep (SCOPA-Sleep) from baseline to the end of the 2-week and 6-week treatment period.

Amendment 04, Final Version 1.0
Protocol No.: BB-2001-201b
EudraCT No.: 2017-000877-35
Page 37 / 142

• Mean absolute change in the Parkinson's Disease Sleep Scale (PDSS-2) from baseline to the end of the 2-week and 6-week treatment period.

- Mean absolute change in the Maintenance of Wakefulness Test (MWT) from baseline to the end of the 6-week treatment period.
- Mean absolute change in the polysomnography from baseline to the end of the 6-week treatment period.

Efficacy in Parkinson's disease (PD):

- Mean absolute change in the UDPRS scale Part III (motor control) from baseline to the end of the 2-week and 6-week treatment period.
- Mean absolute change in the depression HAM-D score from screening/baseline to the end of the the 2-week and 6-week treatment period and safety follow-up.
- Mean absolute change in the Montreal Cognitive Assessment MoCA score from screening/baseline to the end of the 6-week treatment period.
- Mean absolute change in the Fatigue Severity Scale FSS score from screening/baseline to the end of the 6-week treatment period.

The safety of Bayisant compared to placebo will be assessed by the evaluation of the following:

- Incidence of Adverse Events (AEs), Serious Adverse Events (SAEs), and Adverse Events of Special Interest (AESIs) such as headache, nausea and insomnia
- Incidence of suicidal ideation (C-SSRS) findings from screening/baseline to the end of the 2-week and the 6-week treatment period and safety follow-up

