The Bavisant doses for this study have been selected based on data from previous preclinical and clinical research and are lower than the previously anticipated maximum clinical dose of 10 mg/d (for more details, please refer to the Investigator Brochure Ed. 9, 2017). Bavisant has been evaluated at dosages of 10 mg/d or lower in a total of 9 clinical trials and 481 subjects: 4 phase 1 studies in healthy adult subjects, 1 study in healthy elderly subjects, a phase 1 study in Japanese healthy adult male subjects, 2 phase 1 studies in children with ADHD, and a phase 2b study in adult subjects with ADHD. Bavisant has also been used at dosages higher than 10 mg/d in 5 clinical trials and 198 subjects: 4 phase 1 studies in healthy adult subjects and a phase 2a study in men with ADHD. No relevant safety issues are expected since the most common treatment emergent adverse events reported (at least 5%) in the Bavisant 10 mg/d group compared to placebo were: middle insomnia (27.4% vs 0%), initial insomnia (24.7% vs 6.8%), nausea (19.2% vs 1.4%), abnormal dreams (17.8% vs 0%), insomnia (15.1% vs 4.1%), dizziness (12.3% vs 0%), and dysgeusia (12.3% vs 0%). Levels of these events at 1 and 3 mg were lower than at 10mg/d.

The Epworth Sleepiness Scale (ESS) has been selected for the evaluation of the study primary endpoint because this is a well-established validated tool for assessing EDS. Normal range is between 0 and 10 (2.5 and 97.5 percentiles) which corresponds to "lower normal" (0-5) and "higher normal" (6-10). Other ranges can be interpreted as "mild excessive" (11-12), "moderate excessive" (13-15) and "severe excessive" (16-24); so in order to control the variability of the

Protocol No.: BB-2001-201b EudraCT No.: 2017-000877-35 Amendment 04, Final Version 1.0 07/Nov/2018 Page 41 / 142

ESS, the current study requests the categories of either "moderate excessive" or "severe excessive" ESS for the study (>12). As the ESS questionnaire is not suitable for use among people with serious cognitive impairment, correspondingly subjects with evidence of significant cognitive impairment will be excluded from the study (MoCA score  $\leq 22$ ).

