# 8.4.1.14.3 Parkinson's Disease Sleep Scale (PDSS-2)

The Parkinson's Disease Sleep Scale revised version 2 (PDSS-2) is one of the secondary efficacy endpoints and will be assessed at baseline (day -1), visit 2 (day 14), and visit 3 (day 42) or early termination.

The Parkinson's Disease Sleep Scale (PDSS) is a scale for the assessment of sleep disorders in PD in the past week. The scale has 15 items and subjects mark their response to each item on a 10-cm visual analogue scale (VAS). All PDSS items are focussed on nocturnal sleep, except item 15 which addresses DS. The total score is the sum of the item scores and the maximum is 150.

The Revised Version PDSS-2 was developed in order to extend the spectrum of PDSS regarding nocturnal disabilities and for an easier use for subjects as the answers are rated in 5 categories (from 0 [never] to 4 [very frequent]). PDSS-2 total score ranges from 0 (no disturbance) to 60 (maximum nocturnal disturbance). The scale was originally validated in both English and German, and further language validations were performed by Mapi Research Trust (https://eprovide.mapi-trust.org/instruments/parkinson-s-disease-sleep-scale-2#languages). A PDSS-2 sample questionnaire has been included in Appendix 18.5.

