# Treatment Visit 2 (Day 14 ±2)

This visit will be performed 2 weeks after the 1st treatment administration (Day 1). The following examinations/procedures will be performed:

- Vital signs (including heart rate and blood pressure)
- Assessment of sleepiness scales: ESS, SCOPA-Sleep, PDSS-2
- Other scales: UPDRS Part III, C-SSRS, HAM-D, BPRS+
- Dispensing of double blind study medication
- Drug return and accountability
- Recording of adverse events
- Recording of concomitant medication

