# 8.4.5 Secondary Variables

Secondary variables will assess the efficacy on both the excessive daytime sleepiness and PD concomitant conditions:

Efficacy in Excessive Daytime Sleepiness (EDS):

- Mean absolute change in the Epworth Sleepiness Scale (ESS) from baseline to the end of the 2-week treatment period.
- ESS clinical response, defined as ESS absolute decrease from baseline of at least 3.0 points, after 2 and 6 weeks of treatment.
- ESS clinical response, defined as ESS  $\leq$  10 after 2 and 6 weeks of treatment.
- ESS clinical response, defined as either ESS  $\leq$  10 after 2 and 6 weeks of treatment or ESS absolute decrease from baseline of at least 3.0 points after 2 and 6 weeks of treatment.
- Mean relative change in the Epworth Sleepiness Scale (ESS) from baseline to the end of the 2-week and 6-week treatment periods (percentage of absolute decrease compared to baseline ESS).
- Mean absolute change in the Scales for Outcome in Parkinson's Disease Sleep (SCOPA-Sleep) from screening/baseline to the end of the 2-week and 6-week treatment period.
- Mean absolute change in the Parkinson's Disease Sleep Scale (PDSS-2) from screening/baseline to the end of the 2-week and 6-week treatment period.
- Mean absolute change in the Maintenance of Wakefulness Test (MWT) from baseline to the end of the 6-week treatment period.
- Mean absolute change in the polysomnography from baseline to the end of the 6-week treatment period.

Amendment 04, Final Version 1.0 Protocol No.: BB-2001-201b EudraCT No.: 2017-000877-35

Efficacy in Parkinson's disease (PD):

Mean absolute change in the MDS-UDPRS scale Part III (motor control) from screening/baseline to the end of the 2-week and 6-week treatment period.

07/Nov/2018

Page 63 / 142

- Mean absolute change in the depression HAM-D score from baseline to the end of the 2week and 6-week treatment period and safety follow-up.
- Mean absolute change in the Montreal Cognitive Assessment MoCA score from screening/baseline to the end of the 6-week treatment period.
- Mean absolute change in the Fatigue Severity Scale FSS score from screening/baseline to the end of the 6-week treatment period.

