#### 18.6. Parkinson's Disease Sleep Scale (PDSS-2)

122.	Parkinson's	Disease	Sleep	Scale	(PDSS-2	2)

Please rate the severity of the following based on your experiences during the past week (7 days). Please make a cross in the answer box

		Very often (This means 6 to 7 days a week)	Often (This means 4 to 5 days a week)		Occasionally (This means 1 day a week)	Never
1)	Overall, did you sleep well during the last week?	$\square_0$	$\square_1$	$\square_2$	$\square_3$	$\square_4$
2)	Did you have difficulty falling asleep each night?	$\square_4$	$\square_3$	$\square_2$	$\square_1$	$\square_0$
3)	Did you have difficulty staying asleep?	$\square_4$	$\square_3$	$\square_2$	$\square_1$	$\square_{0}$
4)	Did you have restlessness of legs or arms at nights causing disruption of sleep?	$\square_4$	$\square_3$	$\square_2$	$\square_1$	$\square_{0}$
5)	Was your sleep disturbed due to an urge to move your legs or arms?	$\square_4$	$\square_3$	$\square_2$	$\square_1$	$\square_{0}$
6)	Did you suffer from distressing dreams at night?	$\square_4$	$\square_3$	$\square_2$	$\square_1$	$\square_{0}$
7)	Did you suffer from distressing hallucinations at night (seeing or hearing things that you are told do not exist)?		$\square_3$			
8)	Did you get up at night to pass urine?	$\square_4$	$\square_3$	$\square_2$	$\square_1$	$\square_{0}$
9)	Did you feel uncomfortable at night because you were unable to turn around in bed or move due to immobility?	$\Box_4$	$\square_3$		$\square_1$	
10)	Did you feel pain in your arms or legs which woke you up from sleep at night?	$\square_4$	$\square_3$	$\square_2$	$\square_1$	$\square_0$
11)	Did you have muscle cramps in your arms or legs which woke you up whilst sleeping at night?	$\square_4$	$\square_3$		$\square_1$	$\square_0$
12)	Did you wake early in the morning with painful posturing of arms and legs?	$\square_4$	$\square_{\mathfrak{z}}$	$\square_2$	$\square_1$	$\square_0$
13)	On waking, did you experience tremor?	$\square_4$	$\square_3$	$\square_2$	$\square_1$	$\square_{0}$
14)	Did you feel tired and sleepy after waking in the morning?	$\square_4$	$\square_3$			$\Box_{\mathfrak{o}}$
15)	Did you wake up at night due to snoring or difficulties with breathing?	$\square_4$	$\square_3$	$\square_2$	$\square_1$	$\square_0$

Reproduced from Trenkwalder et al (Movement Disorders, Vol. 26, No. 4, 2011)

Amendment 04, Final Version 1.0 07/Nov/2018 Page 111 / 142

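### PDSS-2 rates the night but is filed under daytime-sleepiness efficacy, and its insomnia and dream items are used only inside the summed efficacy total

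*Protocol*

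**What the plan says.** Protocol 6.2.2 and 8.4.5 both open a list headed "Efficacy in Excessive Daytime Sleepiness (EDS" and include PDSS-2 in it; 6.2.2 words the endpoint as "Mean absolute change in the Parkinson's Disease Sleep Scale (PDSS-2) from baseline to the end of the 2-week and 6-week treatment period". The lists for Visits 1, 2 and 3 in 8.4.2 carry the line "Assessment of sleepiness scales: ESS, SCOPA-Sleep, PDSS-2".

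Protocol 8.4.1.14.3 describes the construct differently: "PDSS-2 total score ranges from 0 (no disturbance) to 60 (maximum nocturnal disturbance". Its only mention of a daytime item, "All PDSS items are focussed on nocturnal sleep, except item 15 which addresses DS", comes in the description of the older visual-analogue PDSS, before the text turns to PDSS-2.

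The form in Appendix 18.6 has 15 items about the past week. Item 2 asks "Did you have difficulty falling asleep each night", item 3 asks about staying asleep, and item 6 asks "Did you suffer from distressing dreams at night". Item 7 covers distressing night hallucinations, item 14 tiredness and sleepiness on waking, and item 15 snoring or breathing difficulty.

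Protocol 5.2 names insomnia and abnormal dreams among the drug's common, dose-related adverse events. Protocol 7.2 gives rates for 10 mg/d against placebo, including "middle insomnia (27.4% vs 0%), initial insomnia (24.7% vs 6.8%), nausea (19.2% vs 1.4%), abnormal dreams (17.8% vs 0"%. It says that rates at 1 and 3 mg were lower, without figures.

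SAP 9.2.3 sums the 15 items, and SAP 10.2 analyses the change by ANCOVA as a secondary efficacy endpoint. Neither the protocol's safety variables (8.4.7) nor SAP sections 11 and 12 mention PDSS-2.

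**The concern.** There are two linked problems.

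The first is the construct. A scale that rates the night cannot show an effect on daytime sleepiness in either direction. If it stays in the EDS list, worse nights on a wake-promoting drug may be read as failure on EDS, and better nights as supporting evidence. The secondary objective names sleepiness, motor control and depression as efficacy domains; night-time sleep is none of these.

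The second is lost information. Three items ask patients directly about the kind of event the sponsor already expects from the drug, with a Day -1 baseline and Week 2 and Week 6 values in every arm. In a dose-finding trial that is useful descriptive tolerability data. The plan uses it only as one fifth of a sum labelled efficacy.

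**Working it through.** **1. Reproduce the protocol's maximum.** 15 items × 4 points = 60, which agrees with 8.4.1.14.3.

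**2. Share of the total, from the form in Appendix 18.6.**
- Sleepiness, item 14 only, and only on waking: 4/60 = 6.7%.
- Items 2, 3 and 6: 3 × 4 = 12 points; 12/60 = 20%.
- With item 7 added: 16/60 = 26.7%.

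The daytime item mentioned in 8.4.1.14.3 does not raise the sleepiness share. It belongs to the older scale, and item 15 of the form in use concerns snoring and breathing.

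**3. Match the items to the reported events.**
- Item 2 (falling asleep) matches initial insomnia: 24.7% vs 6.8%, excess 24.7 − 6.8 = 17.9 points.
- Item 3 (staying asleep) matches middle insomnia: 27.4% vs 0%, excess 27.4.
- Item 6 (distressing dreams) matches abnormal dreams: 17.8% vs 0%, excess 17.8.

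All are 10 mg/d rates. They establish that the content overlaps, not how large the effect is at the doses studied.

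**4. Where the same content appears elsewhere.**
- Insomnia: a named adverse event of special interest (protocol 6.2.2 and 8.4.7, SAP 11); HAM-D items 4 to 6; the SCOPA-Sleep night-time items.
- Hallucinations: BPRS+ item 12, analysed in SAP 12.3 within a four-item total.
- Dreams: adverse-event reporting only. No other scheduled scale has a dream item.

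**5. Direction of the score.** On the form, items 2 to 15 score 4 for very often and 0 for never, and item 1 (slept well) scores 0 for very often and 4 for never. A higher total is worse, consistent with 8.4.1.14.3. SAP 9.2.3 codes 0 for very often to 4 for never and then reverses item 1. Every item is therefore 4 minus its form score, so

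SAP total = 15 × 4 − form total = 60 − form total.

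A check on 1,000 random response sets gave form total + SAP total = 60 in every case. Example: a patient who moves from never to very often on item 6, with all else unchanged, changes by +4 on the form and by −4 under the SAP. SAP 9.2.3 states no direction of benefit; SAP 9.1 states that a negative ESS change is improvement. A reader who carried that rule over to PDSS-2 would read more distressing dreams as benefit.

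**The case against.** The strongest reply is that this is little more than a label. ESS is the primary endpoint. PDSS-2 is one of many secondary endpoints, with no hierarchy, no multiplicity adjustment and no success claim attached. The SAP gives it a subsection of its own, with no EDS heading, and describes it as a scale of sleep disorders in Parkinson's disease. On the form's scoring, more insomnia or dreams raises the total and counts against the drug, so harm does not produce a false gain. All of this stands. It limits the weight of the point, but the protocol headings still govern what a PDSS-2 result may be said to show.

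A reader might go further in four ways that the documents do not support.

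- *That the tolerability signal is absent from safety.* It is not. Insomnia is an adverse event of special interest, all adverse events are recorded whatever the suspected cause (protocol 9.7) and summarised by preferred term (11.1.7), and BPRS+ covers hallucinations. Only the PDSS-2 item responses are unused. They still add something: abnormal dreams are not of special interest, and protocol 9.1.2 keeps intermittent events of pre-existing conditions or underlying disease out of the adverse-event record, so reporting depends on judgement against each patient's background.
- *That the shift in the total can be sized.* The three excesses sum to 17.9 + 27.4 + 17.8 = 63.1 events per 100 subjects. At an assumed 1 to 3 points per event, that is 0.63 to 1.89 points of 60. This does not carry over. The rates are for 10 mg/d, the points per event are assumed, and cumulative incidence is not item change on a past-week scale. The documents also give no PDSS-2 standard deviation or meaningful-change threshold.
- *That dose selection is compromised.* No dose-selection rule in the plan uses PDSS-2.
- *That PDSS-2 alone mixes insomnia into an efficacy score.* The SCOPA-Sleep night-time items and the HAM-D insomnia items do the same.

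**Conclusion.** The point holds in limited form. PDSS-2 is misfiled: 7% of its total concerns sleepiness, and then only on waking, so a PDSS-2 result is not evidence on EDS in either direction. Items matching the drug's reported insomnia and abnormal dreams make up 20% of the total and reach the analysis only within that sum. The dream item is the one that no other scheduled scale duplicates.

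The opposite item coding in SAP 9.2.3 is a plain contradiction with the form and could reverse the reading of the result if it is not reconciled.

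The primary analysis is untouched. These conclusions rest on the item wording and scoring in Appendix 18.6 and need no assumed effect size; the size of any shift at 0.5 to 3 mg cannot be derived from the documents.

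**What to change.** 1. In protocol 6.2.2 and 8.4.5, and in the visit lists of 8.4.2, move PDSS-2 to a separate night-time sleep heading. State there and in SAP 9.2.3 that it does not support an EDS claim. SAP 10.2 lists it without an EDS heading and needs no move.
2. In protocol 8.4.1.14.3, make clear that the daytime item 15 belongs to the older PDSS and not to the form in use.
3. In SAP section 12, add one descriptive table of items 2, 3, 6 and 7 by arm: baseline, Weeks 2 and 6, and shift from baseline, presented as supportive tolerability data.
4. In SAP 9.2.3, reconcile the item coding with the Appendix 18.6 form and state which direction is improvement.

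The cost is wording plus one table from data already collected. The downside is one fewer endpoint under EDS efficacy.

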#### 18.7. Scales for Outcome in Parkinson's Disease Sleep (SCOPA-Sleep)

#### SCOPA-SLEEP SCALE

#### Aim of the Questionnaire

By means of this questionnaire, we would like to find out to what extent *in the past month* you have had problems with sleeping. Some of the questions are about problems with sleeping at night, such as, for example, not being able to fall asleep or not managing to sleep on. Another set of questions is about problems with sleeping *during the day*, such as dozing off (too) easily and having trouble staying awake.

#### First read these instructions before you answer the questions!

Place a cross in the box above the answer which best reflects your situation. If you wish to change an answer, fill in the 'wrong' box and place a cross in the correct one. If you have been using sleeping tablets, then the answer should reflect how you have slept while taking these tablets.

#### **NS: Nighttime Sleep Problems**

response options: not at all -a little -q uite a bit -a lot

#### In the past month, ...

- 1. ... have you had trouble falling asleep when you went to bed at night?
- 2. ... to what extent do you feel that you have woken too often?
- 3. ... to what extent do you feel that you have been lying awake for too long at night?
- 4. ... to what extent do you feel that you have woken up too early in the morning?
- 5. ... to what extent do you feel you have had too little sleep at night?

#### Overall, how well have you slept at night during the past month?

response options: very well – well – rather well – not well but not badly - rather badly – badly - very badly

#### **DS: Daytime Sleepiness**

response options: never – sometimes – regularly – often

- 1. How often in the past month have you fallen asleep unexpectedly either during the day or in the evening?
- 2. How often in the past month have you fallen asleep while sitting peacefully?
- 3. How often in the past month have you fallen asleep while watching TV or reading?
- 4. How often in the past month have you fallen asleep while talking to someone?
- 5. In the past month, have you had trouble staying awake during the day or in the evening?
- 6. In the past month, have you experienced falling asleep during the day as a problem?

Reproduced from Marinus et al (SLEEP 2003;26(8):1049-54)

Amendment 04, Final Version 1.0 07/Nov/2018 Page 112 / 142

Protocol No.: BB-2001-201b EudraCT No.: 2017-000877-35

#### 18.8. Unified Parkinson's Disease Rating Scale Part III (UPDRS Part III)

#### III. MOTOR EXAMINATION

#### Speech

0-normal

- 1-slight loss of expression, diction, volume
- 2-monotone, slurred but understandable, mod. impaired
- 3-marked impairment, difficult to understand
- 4-unintelligible

#### **Facial Expression**

- 0-Normal
- 1-slight hypomymia, could be poker face
- 2-slight but definite abnormal diminution in expression
- 3-mod. hypomimia, lips parted some of time
- 4-masked or fixed face, lips parted 1/4 of inch or more with complete loss of expression

#### **Tremor at Rest**

#### + Face

0-absent

- 1-slight and infrequent
- 2-mild and present most of time
- 3-moderate and present most of time
- 4-marked and present most of time

#### + Right Upper Extremity (RUE)

0-absent

- 1-slight and infrequent
- 2-mild and present most of time
- 3-moderate and present most of time
- 4-marked and present most of time

#### + LUE

0-absent

- 1-slight and infrequent
- 2-mild and present most of time
- 3-moderate and present most of time

#### Amendment 04, Final Version 1.0 07/Nov/2018

Page 113 / 142

## BenevolentBio

Protocol No.: BB-2001-201b EudraCT No.: 2017-000877-35

4-marked and present most of time

#### + RLE

- 0-absent
- 1-slight and infrequent
- 2-mild and present most of time
- 3-moderate and present most of time
- 4-marked and present most of time

#### + LLE

- 0-absent
- 1-slight and infrequent
- 2-mild and present most of time
- 3-moderate and present most of time
- 4-marked and present most of time

#### **Action or Postural Tremor**

#### + RUE

- 0-absent
- 1-slight, present with action
- 2-moderate, present with action
- 3-moderate present with action and posture holding
- 4-marked, interferes with feeding

#### + LUE

- 0-absent
- 1-slight, present with action
- 2-moderate, present with action
- 3-moderate present with action and posture holding
- 4-marked, interferes with feeding

#### **Rigidity**

#### + Neck

- 0-absent
- 1-slight or only with activation
- 2-mild/moderate
- 3-marked, full range of motion

Page 114 / 142

Protocol No.: BB-2001-201b EudraCT No.: 2017-000877-35

4-severe

